**Table 1: Treatment Cohorts and Planned Enrollment**

Cohort	PCI-32765 (mg/day)	Dexamethasone	Planned First Stage Enrollment	CBR Criteria for First Stage	Total Enrollment (First and Second Stages)
1	420	Upon PD, 40 mg once weekly is allowed †	11*	$\geq 2$	35
2	560	40 mg once weekly	18	$\geq 3$	43
3	840	Upon PD, 40 mg once weekly is allowed †	18	$\geq 3$	43
4	840	40 mg once weekly	18**	$\geq 3$	43

\* n=11 planned for Cohort 1 First Stage, n=13 were enrolled. The decision for second stage expansion will be based on the number of CBR in the first 11 subjects.

[figure not shown]
\*\* n=18 planned for Cohort 4 First Stage, n=20 were enrolled. The decision for second stage expansion will be based on the number of CBR in the first 18 subjects.

† For Cohorts 1 and 3 subjects who have confirmed PD, and who are clinically stable, without significant worsening of symptoms or hematologic status (ie, meet all entry criteria for the study in regard to symptoms and hematology), will be eligible to receive dexamethasone 40 mg orally once per week in addition to continued treatment with PCI-32765, at the discretion of the investigator.

Subjects are allowed to continue study drug as long as the subject is clinically stable (SD or better) and the subject is not experiencing any unacceptable toxicity. Subjects in the monotherapy cohorts (1 and 3) who have PD confirmed as required by definition in [Appendix 5](#), and without significant worsening of symptoms or hematologic status (ie, meet all entry criteria for the study in regard to symptoms and hematology), will be eligible to receive dexamethasone 40 mg p.o. once per week in addition to continued treatment with PCI-32765, at the discretion of the investigator. Otherwise, subjects having PD will be removed from study.

A flowchart summary of the PCYC-1111-CA study design is provided in Section 4.1.1. For a complete description of procedures refer to Study Procedures ([Section 7.0](#)).

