### 7.1.4 Follow-up for Progression and Survival

Subjects who discontinue from the study treatment for reasons other than PD will be followed for Response Follow-up (RFU) approximately every 2 months until PD or start use of alternative antineoplastic therapy. During this period, the following tests may be performed at the investigator's discretion as standard of care:

- M-protein evaluations:
  - UPEP and SPEP
  - Serum IFE
  - Serum FLC
  - quantitative immunoglobulins
- Plasmacytoma evaluation
- Bone radiological assessment
- Serum chemistries including calcium and albumin

A bone marrow aspirate sample at the time of confirmed progression will be collected during this period prior to the start of a new antineoplastic treatment. Refer to [Section 4.3](#) for description of testing.

A minimum of one Long Term Follow Up visit will be performed. Further Long-term Follow-up assessments will no longer be collected.

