### Confirmation of Response Categories

In order to be classified as a hematologic response, confirmation of serum monoclonal protein, serum immunoglobulin free light chain (when primary determinant of response) and urine monoclonal protein (when primary determinant of response) results must be made by verification on two consecutive determinations. Confirmation assessments may be performed at any time after the initial assessment.

- Bone marrow aspirate/biopsy is **only** required to document CR or sCR, except for subjects with bone marrow plasmacytosis evaluable disease **only**, where a bone marrow is required to document all response categories including progression. However, a second confirmatory bone marrow is not required to confirm response in any case
- Radiographic studies are not required to satisfy these response requirements; however, if radiographic studies were performed there should be no evidence of progressive or new bone lesions.

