8.8. Efficacy Analyses

Starting from Cycle 2, subjects will be evaluated by the investigators per the modified IMWG response criteria. Confirmation of investigator-assessed responses by an independent review committee (IRC) may be done as a supportive assessment. The method of independent review will be governed by an IRC charter, if needed. Some or all of the following assessments may be required to confirm the response categories: M-protein evaluations (UPEP and SPEP, serum and urine IFE, serum FLC), plasmacytoma evaluation, bone radiological assessment, bone marrow aspiration and biopsy, and serum chemistries including calcium and albumin.

The all treated population is the primary population for the efficacy endpoints. Unless specified otherwise, the all treated population will be used for all efficacy analyses. Response rates (CBR rate and ORR) will also be analyzed based on response evaluable population and will be considered as sensitivity analyses. Only adequate response assessments will be included in the analysis. An adequate response assessment is one for which the response assignment is sCR, CR, VGPR, PR, MR, SD or PD (i.e. not UE/Unknown).

IMWG criteria specify that all response categories require confirmation from a second consecutive assessment made at any time after the initial assessment with the exception of sCR and CR. The initial sCR or CR will be reported as confirmed response. However, if a subject has only one adequate post baseline assessment for which the response assignment is MR, PR or VGPR, then the best response will be summarized as SD.

In Cohorts 1 and 3, subjects will be on ibrutinib monotherapy and may convert to ibrutinib and dexamethasone combination therapy at the discretion of the investigator after a confirmed PD on ibrutinib monotherapy. Thus the efficacy endpoints (CBR, DCB, ORR, DOR, PFS, and TTP) will be presented and distinguished as with and without dexamethasone for subjects in Cohorts 1 and 3, when applicable.

No inferential statistical comparisons among treatment cohorts will be performed in this study.

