8.8.2. Secondary Efficacy Endpoints

8.8.2.1. Duration of Clinical Benefit (DCB)

For all cohorts, DCB will be computed for those subjects with confirmed responses (MR or better) prior to initiation of new antineoplastic therapy. DCB will be calculated from the first observation of response (before confirmation) to the time of PD (earliest occurrence), with death from causes other than progression censored.

PD based upon changes in monoclonal protein levels requires confirmation. No minimal time interval between assessments is stipulated. PD based upon bone marrow, bone lytic lesions, or plasmacytoma changes, or upon development of hypercalcemia attributed to multiple myeloma do not require confirmation. DCB will be right-censored for subjects who meet one or more of the censoring conditions listed in Table 4 below.

Similarly, for Cohorts 1 and 3 ibrutinib monotherapy, DCB will be computed for those subjects with confirmed responses (MR or better) prior to initiation of dexamethasone or new antineoplastic therapy, whichever occurs first.

Table 4: Date of Event and Censoring Rules for DCB Analysis

Row	Situation	Date of Event or Censoring	Outcome
Events include death due to progression or first documentation of confirmed PD that occurred on or prior to the data analysis cutoff date. For Cohorts 1 and 3 ibrutinib monotherapy, events need to meet one additional criterion: occurred at or prior to initiation of dexamethasone.			
1.1	Death due to progression or confirmed PD documented at scheduled disease assessments or between two scheduled disease assessments.	Earliest date of adequate disease assessment documenting confirmed PD or date of death due to progression, whichever occurs first.	Progressed
1.2	Death before first disease assessment	Date of death	Progressed
All other cases will be censored as follows:			
2.1	No baseline assessment	Date of first study treatment	Censored
2.2	No adequate post-baseline assessment (including lost to follow-up since enrollment)	Date of first study treatment	Censored
2.3	Not known to have confirmed PD or died due to progression at the data analysis cutoff date (this includes subjects who were known to have confirmed PD or died after the data analysis cutoff date)	Date of last adequate disease assessment showing no evidence of confirmed PD on or before data analysis cutoff date	Censored
2.4	Addition of dexamethasone (Cohorts 1 and 3 ibrutinib monotherapy only)	The start date of dexamethasone	Censored

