8.8.3. Exploratory Efficacy Endpoints

8.8.3.1. Progression-free Survival (PFS)

PFS is defined as the duration from the start of study treatment to PD (earliest occurrence) or death (regardless of cause of death), whichever comes first. The calculation for the time of PD will be the same as that for DCB (Section 8.7.2.1).

PFS will be right-censored for subjects who meet one or more of the censoring conditions listed in Table 5 below.

Table 5: Date of Event and Censoring Rules for PFS Analysis

Row	Situation	Date of Event or Censoring	Outcome
Events include death or first documentation of confirmed PD that occurred on or prior to the data analysis cutoff date. For Cohorts 1 and 3 ibrutinib monotherapy, events need to meet one additional criterion: occurred at or prior to initiation of dexamethasone.			
1.1	Death or confirmed PD documented at scheduled disease assessments or between two scheduled disease assessments.	Earliest date of adequate disease assessment documenting confirmed PD or date of death due to progression, whichever occurs first.	Progressed
1.2	Death before first disease assessment	Date of death	Progressed
All other cases will be censored as follows:			
2.1	No baseline assessment	Date of first study treatment	Censored
2.2	No adequate post-baseline assessment (including lost to follow-up since enrollment)	Date of first study treatment	Censored
2.3	Not known to have confirmed PD or died at the data analysis cutoff date (this includes subjects who were known to have confirmed PD or died after the data analysis cutoff date)	Date of last adequate disease assessment showing no evidence of confirmed PD on or before data analysis cutoff date	Censored
2.4	Addition of dexamethasone (Cohorts 1 and 3 ibrutinib monotherapy only)	The start date of dexamethasone	Censored

For subjects who meet more than one censoring condition, PFS will be censored according to the earliest censoring condition. For subjects who meet none of the censoring conditions, PFS will be calculated using the earliest event date.

$\text{PFS Event (day)} = \text{Date of PFS event} - \text{Date of first study treatment}$

$\text{PFS Censor (day)} = \text{Date of censoring} - \text{Date of first study treatment} + 1$

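### The SAP has no rule for a single, never-repeated M-protein progression, so some progressors may be censored on the day they progress and DCB, DOR, PFS and TTP may be overstated

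*SAP*

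**What the plan says.** **Event rule.** SAP 8.8.2.1 (DCB) says "PD based upon changes in monoclonal protein levels requires confirmation" and adds "No minimal time interval between assessments is stipulated". Other routes to progression are exempt: "PD based upon bone marrow, bone lytic lesions, or plasmacytoma changes, or upon development of hypercalcemia attributed to multiple myeloma do not require confirmation". DOR (8.8.2.3), PFS (8.8.3.1) and TTP (8.8.3.2) adopt this timing of PD by cross-reference.

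**Censoring rule.** Row 2.3 of Tables 4 and 5 covers subjects with no confirmed PD and no qualifying death. The censoring date is "Date of last adequate disease assessment showing no evidence of confirmed PD on or before data analysis cutoff date". SAP 8.8 defines what is adequate: "An adequate response assessment is one for which the response assignment is sCR, CR, VGPR, PR, MR, SD or PD (i.e. not UE/Unknown").

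**Confirmation.** Appendix 5 of the protocol says "Confirmation assessments may be performed at any time after the initial assessment". Its footnote a requires the two consecutive assessments to come before any new therapy.

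**Stopping and follow-up.** Protocol 6.6 makes withdrawal mandatory on confirmed PD. Section 6.3.1 continues drug until PD, without the qualifier. Section 4.1 first speaks of PD confirmed under Appendix 5 for Cohorts 1 and 3, then says "Otherwise, subjects having PD will be removed from study". Section 7.1.4 says "Subjects who discontinue from the study treatment for reasons other than PD will be followed for Response Follow-up (RFU"). According to the synopsis, subjects who stop because of PD are followed for survival.

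**The concern.** The tables have no row for one M-protein PD that is never repeated and is followed by stopping drug, changing therapy or death. SAP 8.8 does settle the matching case for response: a subject whose only adequate post-baseline assessment is MR, PR or VGPR is summarized as SD. It says nothing about a single PD.

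By default such a subject falls into row 2.3. The censoring then happens because the subject appears to have progressed, so the Kaplan-Meier assumption that censoring is unrelated to the event fails, and it fails in one direction. At stake is the credibility of the reported medians and landmark rates for two secondary endpoints (DCB, DOR) and two exploratory ones (PFS, TTP).

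**Working it through.** **1. Following one subject through the rules.** The last disease assessment shows M-protein PD and no second sample is assigned a response.
- The PD is unconfirmed, so it is not an event (SAP 8.8.2.1).
- The visit was assigned PD, so it is adequate (SAP 8.8).
- It shows no *confirmed* PD, so it meets row 2.3 and is the latest such visit. The subject is censored on the PD date.
- If a death is recorded by the cutoff, it becomes the event: any death for PFS, death due to progression for DCB, DOR and TTP. The event then falls later than the progression.
- In the Cohorts 1 and 3 monotherapy analysis, row 2.4 also censors at the start of dexamethasone, and the earliest censoring condition applies.

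In each case the recorded time is either censored at progression or longer than the time to progression.

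**2. Can it happen under the protocol?**
- *Limiting it:* 6.6 ties mandatory withdrawal to confirmed PD. A repeat sample has no minimum interval. 6.3.3.1 asks for confirmation or a repeat sample before dexamethasone is added. Under 7.1.3, each subject has a Safety Follow-up visit.
- *Allowing it:* 4.1 and 6.3.1 can be read as stopping at a first PD. Response Follow-up excludes subjects who stop for PD. A prompt change of therapy closes the confirmation window (Appendix 5, footnote a). From Cycle 12, visits are every second 28-day cycle, so the next scheduled sample may be 2 × 28 = 56 days away. Long-term follow-up is cut to a minimum of one visit (7.1.4), so a later death may not be captured.

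**3. Size.** The plan states no expected median, event count or power for these four endpoints, so there is no figure to reproduce. The documents also do not say how many progressions stay unconfirmed. What follows is an illustration.

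Let λ be a constant progression hazard and f the fraction of *all* progressions that are unconfirmed and censored at the PD date. Then:
- recorded event hazard = (1-f)λ
- Kaplan-Meier estimates S(t)^(1-f)
- estimated median = ln 2 / [(1-f)λ] = true median / (1-f)

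For scale only, I use 2.8 and 4.7 months. These are the lowest and highest of the TTP figures for high-dose dexamethasone cited in Protocol 2.5; they are not predictions for this trial.

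| f (assumed) | 1/(1-f) | 2.8 months becomes | 4.7 months becomes |
|---|---|---|---|
| 0 | 1.00 | 2.8 | 4.7 |
| 10% | 1/0.9 = 1.11 | 3.1 | 5.2 |
| 20% | 1/0.8 = 1.25 | 3.5 | 5.9 |
| 30% | 1/0.7 = 1.43 | 4.0 | 6.7 |

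A Kaplan-Meier simulation with 400,000 subjects per scenario agrees with these factors.

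If instead every such subject has a later death counted as the event, at an assumed median of 6 to 18 months after PD, the simulated factors are 1.12–1.16, 1.25–1.37 and 1.40–1.67. A recorded death therefore does not remove the bias.

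Because only M-protein PD needs confirmation, f is the share of progressions resting on M-protein alone multiplied by the share of those never confirmed. It is smaller than the second share whenever other routes contribute.

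**The case against.** The best defence is that the protocol, followed as written, leaves few unconfirmed progressions. Withdrawal for progression is mandatory on confirmed PD. The sentence just before the 4.1 wording on removal refers to PD confirmed under Appendix 5, so plain PD there and in 6.3.1 may already mean confirmed. A second sample can be taken at any time, and the event is then dated at the first PD with no bias. Requiring confirmation also protects against laboratory error, which Appendix 5 footnote g recognises. All of this stands. It bears on how often the gap is reached, not on whether the tables have one.

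Four stronger readings are tempting, and the documents do not support them:
- *Subjects taken off drug for PD get no further disease assessment.* Each subject has a Safety Follow-up visit. The M-protein row of Appendix 4 appears to include it, although the table is broken in the available text and footnote r names only screening, Cycle 1 Day 1 and the start of each later cycle. The defensible wording is that some subjects may have no confirming assessment.
- *The four durations are overstated.* They may be. At f = 0 there is no bias, and f is not given.
- *Fast progressors are hit hardest.* Hypercalcemia, lytic lesions, plasmacytoma and marrow progression need no confirmation, and deaths count as described above. These routes may capture many such subjects.
- *The confirmed-PD definition should be replaced in the main analysis.* It is the protocol's own definition, and counting single readings in an open-label study has its own risk. The choice is a trade-off, not an error.

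**Conclusion.** The point holds as a gap in the SAP with a known direction and an unknown size. Read together, the confirmation rule, row 2.3 and the definition of an adequate assessment censor a single unrepeated M-protein PD on its own date, or shift the event to a later death. Both effects lengthen DCB, DOR, PFS and TTP.

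The factors 1.11, 1.25 and 1.43 rest on three assumptions: an exponential time to progression, a fraction f that is constant over time, and values of f chosen for illustration. If Protocol 6.6 and the repeat sampling work as intended, f is near zero and so is the bias.

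The primary endpoint, CBR, and the two-stage decision rules count responders and do not use the date of progression, so they are unaffected. The matter deserves action because the remedy is cheap and the bias runs one way.

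**What to change.** - **Keep** the confirmed-PD analysis as the main analysis.
- **Add** to SAP 8.8.2.1 and Tables 4 and 5 a pre-specified sensitivity analysis for DCB, DOR, PFS and TTP. In it, a first M-protein PD not contradicted by a later adequate assessment is an event on its own date when followed by any of: discontinuation with PD as the reason; new antineoplastic therapy (or dexamethasone, in the Cohorts 1 and 3 monotherapy analysis); or death before the next assessment.
- **Report** the number of unconfirmed M-protein progressions per cohort, so that readers can see f instead of assuming it.
- **Reconcile** the use of PD and confirmed PD in Protocol 4.1, 6.3.1 and 6.6. Which reading applies is for the sponsor to settle.

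Cost: SAP wording and some programming. The inputs are already collected or summarized under the SAP: response assignments, reason for discontinuation (8.2.1), subsequent therapy (8.7) and deaths (8.9.1). The sensitivity medians may be shorter than the main ones, and a spurious single reading could count as an event there, which is a reason to keep the confirmed analysis as the main one.

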8.8.2.2. Objective Response Rate (ORR)

Objective response rate (ORR) is defined as the proportion of subjects achieving confirmed responses (PR or better) prior to initiation of new antineoplastic therapy as assessed by investigator per the modified IMWG criteria. ORR and its corresponding 2-sided 90% exact binomial confidence interval will be calculated and presented by treatment cohort.

Subgroup Analysis

The same subgroup analyses will be performed as those for CBR.

8.8.2.3. Duration of Response (DOR)

DOR will include only subjects with confirmed responses (PR or better). DOR will be calculated from the first observation of response (before confirmation) to the time of PD (earliest occurrence), with death from causes other than progression censored. The calculation for the time of PD and censoring rules are the same as those for DCB (see Table 3).

DOR Event (day) = Date of event – Date of first overall response

DOR Censor (day) = Date of censoring – Date of first overall response + 1

The same analyses will be done for DOR as those for DCB described in Section 8.7.2.1.

8.8.3. Exploratory Efficacy Endpoints

8.8.3.1. Progression-free Survival (PFS)

PFS is defined as the duration from the start of study treatment to PD (earliest occurrence) or death (regardless of cause of death), whichever comes first. The calculation for the time of PD will be the same as that for DCB (Section 8.7.2.1).

PFS will be right-censored for subjects who meet one or more of the censoring conditions listed in Table 5 below.

Table 5: Date of Event and Censoring Rules for PFS Analysis

Row	Situation	Date of Event or Censoring	Outcome
Events include death or first documentation of confirmed PD that occurred on or prior to the data analysis cutoff date. For Cohorts 1 and 3 ibrutinib monotherapy, events need to meet one additional criterion: occurred at or prior to initiation of dexamethasone.			
1.1	Death or confirmed PD documented at scheduled disease assessments or between two scheduled disease assessments.	Earliest date of adequate disease assessment documenting confirmed PD or date of death due to progression, whichever occurs first.	Progressed
1.2	Death before first disease assessment	Date of death	Progressed
All other cases will be censored as follows:			
2.1	No baseline assessment	Date of first study treatment	Censored
2.2	No adequate post-baseline assessment (including lost to follow-up since enrollment)	Date of first study treatment	Censored
2.3	Not known to have confirmed PD or died at the data analysis cutoff date (this includes subjects who were known to have confirmed PD or died after the data analysis cutoff date)	Date of last adequate disease assessment showing no evidence of confirmed PD on or before data analysis cutoff date	Censored
2.4	Addition of dexamethasone (Cohorts 1 and 3 ibrutinib monotherapy only)	The start date of dexamethasone	Censored

For subjects who meet more than one censoring condition, PFS will be censored according to the earliest censoring condition. For subjects who meet none of the censoring conditions, PFS will be calculated using the earliest event date.

$\text{PFS Event (day)} = \text{Date of PFS event} - \text{Date of first study treatment}$

$\text{PFS Censor (day)} = \text{Date of censoring} - \text{Date of first study treatment} + 1$

Kaplan-Meier curves will be used to estimate the distribution of PFS. The 50th percentile of Kaplan-Meier estimates will be used to estimate the median PFS. A 2-sided 95% confidence interval (CI) will be provided for this estimate. PFS at landmark time points (e.g. 4, 8, 12, 16 months from first study treatment) will also be estimated with corresponding 2-sided 95% CI.

Subgroup Analysis

Subgroup analyses will be performed for the selected factors (see Section 8.7.1). PFS event rate, Kaplan-Meier estimates for the median and PFS at landmark time (decided by data status

at final analysis) will be provided for each stratum of the subgroups. Forest plot will be provided for PFS at landmark time.

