### **6.3.3 Combination of PCI-32765 and Dexamethasone Dosing**

#### **6.3.3.1 For Subjects with PD (Cohorts 1 and 3)**

At the discretion of the investigator and after Cycle 1, subjects in Cohorts 1 and 3 who have PD and who are clinically stable, without significant worsening of symptoms or hematologic status (ie, meet all entry criteria for the study in regard to symptoms and hematology), will be eligible to receive dexamethasone 40 mg orally once per week in addition to continued treatment with PCI-32765. PD should be confirmed or have repeat laboratory samples collected prior to addition of dexamethasone. Dexamethasone administration may commence at any time during a PCI-32765 cycle. Blood samples for PK should be obtained during the initial cycle with added dexamethasone (Cohort 1 and 3 only), according to [Section 7.1.2](#).

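### In the Cohort 1 and 3 monotherapy analyses, PFS, TTP, DCB and DOR are censored at dexamethasone start even when it was given for M-protein progression that is unconfirmed, or confirmed only later

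*SAP*

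**What the plan says.** SAP 8.8.3.1, Table 5, row 2.4 ("Addition of dexamethasone (Cohorts 1 and 3 ibrutinib monotherapy only") censors monotherapy PFS at the start date of dexamethasone. Row 2.4 of Table 4 (SAP 8.8.2.1) does the same for DCB. TTP (8.8.3.2) and DOR (8.8.2.3) inherit the DCB rules. The DOR text points to Table 3, the performance-status table, where Table 4 is evidently meant.

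Both tables open with a definition of an event. For Cohort 1 and 3 monotherapy, "events need to meet one additional criterion: occurred at or prior to initiation of dexamethasone". In Table 5 the PD event date is "Earliest date of adequate disease assessment documenting confirmed PD", so what counts is the first documentation and not the confirming result. The censoring rows then follow under "All other cases will be censored as follows".

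On confirmation, SAP 8.8.2.1 says "PD based upon changes in monoclonal protein levels requires confirmation". PD shown by marrow, bone lesions, plasmacytoma or hypercalcemia needs none.

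On when dexamethasone may start, Protocol 4.1 (including the Table 1 footnote) and 8.1 describe confirmed PD first. Protocol 6.3.3.1 is looser: "PD should be confirmed or have repeat laboratory samples collected prior to addition of dexamethasone".

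**The concern.** Kaplan-Meier estimation assumes that a censored subject has the same later risk as those still followed. In Cohorts 1 and 3 dexamethasone is added only because the investigator judges that the disease is progressing on ibrutinib alone. Once subjects whose PD meets the event definition are counted as events, those left for row 2.4 were still given dexamethasone for apparent progression, apart from protocol deviations. Censoring them removes likely failures from the event count, so the monotherapy durations read too long.

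Protocol 4.1 describes Cohorts 1 and 3 as testing monotherapy activity. The durations and the landmark PFS values (SAP 8.8.3.1 gives 4, 8, 12 and 16 months as examples) would describe that activity somewhat too favourably.

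**Working it through.** **Step 1: which subjects are affected.** The table takes a Cohort 1 or 3 subject who adds dexamethasone and applies the event definition before the censoring rows.

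| Progression before dexamethasone | Result in the monotherapy analysis |
|---|---|
| Marrow, bone lesion, plasmacytoma or hypercalcemia | Event; no confirmation needed |
| M-protein, confirmed before dexamethasone | Event at first PD date |
| M-protein, repeat sample drawn before dexamethasone, confirming result returned later | Event at first PD date |
| M-protein, confirmed only by a sample taken after dexamethasone | Not stated |
| M-protein, never confirmed | Censored, row 2.4 |

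Only the last two rows are at issue. For the fourth, the SAP does not say whether confirmation obtained after dexamethasone counts. SAP 8.3 ends the monotherapy period on the day before dexamethasone. Footnote a of Protocol Appendix 5 asks for two consecutive assessments before any new therapy, without saying whether added dexamethasone is one.

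**Step 2: inputs.** The documents give no assumed median, event count or power for these four endpoints, so there is no plan figure to reproduce.

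- f, the share of progressions turned into censoring: not in the documents (assumption).
- True monotherapy median: not in the documents. For illustration, 2.8 and 4.7 months, the lowest and highest median TTP that Protocol 2.5 gives for high-dose dexamethasone alone.
- Stage 1 enrollment: 13 (Cohort 1) and 18 (Cohort 3), from Protocol 2.4.5.

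**Step 3: formula.** Let time to progression be exponential with hazard λ and median M = ln 2/λ. If a share f of progressions is recoded as censored at about the same time, the estimated hazard is λ(1-f). The estimated median is then M/(1-f), and PFS at time t is 0.5^(t(1-f)/M).

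**Step 4: plausible f.** As a product of assumed shares: half of progressors receive dexamethasone, 30% of those start before confirmation, and 20% of those repeats fall short. Then f = 0.5 × 0.3 × 0.2 = 0.03. If all start before confirmation, f = 0.5 × 1 × 0.2 = 0.10.

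**Step 5: results.**

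| f | Factor 1/(1-f) | Median, true 2.8 | Median, true 4.7 | 4-month PFS, true 2.8 | 4-month PFS, true 4.7 |
|---|---|---|---|---|---|
| 0 | 1.00 | 2.8 | 4.7 | 0.371 | 0.554 |
| 3% | 1.03 | 2.9 | 4.8 | 0.383 | 0.564 |
| 10% | 1.11 | 3.1 | 5.2 | 0.410 | 0.588 |
| 25% | 1.33 | 3.7 | 6.3 | 0.476 | 0.642 |

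The 25% row shows how the formula behaves and is not an estimate. A simulation of 200,000 subjects, with dexamethasone 0.5 month after PD (assumed), gave medians of 3.14 and 5.27 months at f = 10%. With n = 18, a true median of 2.8 months and no lag, the typical Kaplan-Meier median moved from 2.57 months at f = 0 to 2.96 at f = 10%.

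**Step 6: in subjects.** If every subject progressed, f = 3% would be 0.03 × 13 = 0.4 and 0.03 × 18 = 0.5 subjects, and f = 10% would be 1.3 and 1.8. One subject is 1/13 = 7.7% or 1/18 = 5.6% of a cohort.

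**The case against.** The strongest reply is that the affected case is narrow. It needs PD by M-protein alone, a clinically stable subject, an investigator who chooses dexamethasone, a start before confirmation, and a repeat that falls short or confirmation that comes only later. A subject whose PD is never confirmed has not met the SAP's own definition, and some such rises may be assay variation. The documents also do not show that dexamethasone would mask later M-protein progression: Protocol 2.5 treats a 10% response rate as a likely upper limit for low-dose dexamethasone here. All of this stands, and it limits the size. It does not make the remaining censoring non-informative, because those subjects still received dexamethasone for apparent progression.

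The consequences are also limited. CBR before dexamethasone governs the primary analysis and Stage 2 expansion of Cohorts 1 and 3. PFS and TTP are exploratory, and DCB and DOR are secondary and include responders only. No inferential comparison of cohorts is planned, and results that include the dexamethasone period are presented as well. This stands too.

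A reader might infer the opposite extreme, that everyone who progresses and adds dexamethasone is censored. Two sentences around Table 5 invite this: "PFS will be right-censored for subjects who meet one or more of the censoring conditions listed in Table 5 below" and "For subjects who meet none of the censoring conditions, PFS will be calculated using the earliest event date". SAP 8.8.2.1 has matching sentences for DCB. Taken alone they would censor even confirmed progressors, but the tables do not support that. The censoring rows cover only cases that are not events. The extra criterion tying events to dexamethasone start matters only for subjects who received dexamethasone, and it would have no function if all of them were censored. Nor does starting dexamethasone before the confirming result is known turn an event into censoring, because the event carries the first PD date.

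**Conclusion.** The point holds in a limited form. Row 2.4 censors informatively those Cohort 1 and 3 subjects given dexamethasone for M-protein PD that is never confirmed. It may do the same where PD is confirmed only after dexamethasone starts. Monotherapy PFS, TTP, DCB and DOR then lean upward by a factor of about 1/(1-f) in the median: +3% at f = 3% and +11% at f = 10%. This rests on an exponential model and on an f that the documents do not give and that may be only a few percent. The primary CBR is unaffected. The wording is still worth correcting, because with 13 and 18 subjects in Stage 1 a single recoded subject is 6% to 8% of a cohort.

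**What to change.** 1. In SAP Tables 4 and 5, state that row 2.4 applies only when no PD meeting the event definition was first documented at or before dexamethasone start. State that confirmation obtained after dexamethasone start keeps the first PD date as the event date. Bring the sentences around the tables into line, and point the DOR text to Table 4.
2. Add a sensitivity analysis for Cohorts 1 and 3 that counts dexamethasone start as an event, dated at the assessment that led to it, or at dexamethasone start if there is none. Report it beside the main analysis. It covers the never-confirmed cases, which stay censored in the main analysis. Making them events there would conflict with the confirmed-PD definition and would treat these two cohorts differently from Cohorts 2 and 4.
3. Reconcile Protocol 6.3.3.1 with 4.1 and 8.1 on whether PD must be confirmed before dexamethasone.

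The cost is some wording in the SAP and protocol and one extra analysis. In that analysis some unconfirmed progressions count as events, so the durations will look slightly shorter.
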